#### **4.1 General Concomitant Medication and Supportive Care Guidelines**

Patients will be allowed to continue background DMARDs including methotrexate, leflunomide, azathioprine, mycophenolate mofetil, and/or anti-malarials. These are standard drugs used in the treatment of sarcoidosis. The regimen must be stable for  $\geq$  28 days prior to baseline and remain stable during follow-up. Patients will also be on  $\geq$  10 mg and  $\leq$  60 mg daily of prednisone or equivalent glucocorticoid to be eligible for the study and will follow a scheduled taper. Patients will undergo blood draws during the study. During blood draws, a patient may have pain and/or bruising at the place on his/her arm where blood is taken. Blood clots may form and infections may occur, but these events are rare. He or she may feel faint or lightheaded. They will also have an electrocardiogram. There may be minor discomfort and/or skin irritation at the site where the electrodes (sticky pads) are placed on the skin for the recording of the ECG. They will also have a chest x-ray. Radiation exposure from a chest x-ray is equivalent to the amount of radiation exposure one would experience from 10 days of natural radiation (such as sunlight). They will also have a non-contrast chest computed tomography. Radiation exposure from a computed tomography of the chest is equivalent to roughly 70 times the amount of radiation from a chest x-ray. They will undergo pulmonary function testing. There may be minor discomfort from the deep breathing required to complete pulmonary function testing. If they have known or suspected ocular sarcoidosis, they will have an ophthalmologic evaluation with fluorescein angiography. This will involve dilating the pupils, which often makes it difficult to see clearly and in bright lights after the eye exam for a few hours. For the angiography, patients will receive an injection of a dye called fluorescein. There may be minor discomfort from the needle at the site of injection. There may also be bruising at the site of injection. The most common side effects of this dye are nausea and vomiting; however, occasional allergic reactions, fainting, breathing difficulties, or shock may occur. The dye may stain your skin and urine; which may last approximately for 1 day. Mild reactions such as itching, swelling, or redness near where the dye is put in your vein are more common and have been estimated to happen in about 1 out of 100 times. Rare severe allergic reactions can also happen during the fluorescein dye test. People allergic to shellfish may be at increased risk for an allergic reaction to fluorescein or other dye. However, individuals with allergies to shellfish can receive a medication before the dye test to minimize allergic responses. Serious allergic reactions such as severe swelling and difficulty breathing can happen in 1 out of 10,000 patients and about 1 out of 222,000 patients can have a heart attack, stroke, or even die from the fluorescein dye administration.

#### **4.2 Criteria for Removal from Study**

The study will be placed on hold for safety monitoring board review in the case of a death, a serious adverse event related to the drug, or a Grade 4 treatment emergent adverse event or laboratory

abnormality. The safety monitoring committee will determine if the study can resume and if the patient should remain in the study or be removed. A patient may withdraw from the study at any time if they choose to withdraw their consent.

#### **4.3 Alternatives**

Risks to the patient will be minimized through frequent clinic visits and appropriate laboratory testing. In addition, all data will be reviewed by the investigators, as well as the safety monitoring board, which will meet every 6 months.

### **5. INVESTIGATIONAL AGENT/DEVICE/PROCEDURE INFORMATION**

#### **5.1 Sarilumab**

Sarilumab (SAR153191), also designated as REGN88, is co-developed by Sanofi and Regeneron. Sarilumab is a recombinant human monoclonal antibody of the IgG kappa isotype directed against the alpha subunit of the IL-6 receptor (IL-6R $\alpha$ ). Sarilumab is a potent and specific inhibitor of IL-6 mediated signaling. By binding to IL-6R $\alpha$  with high affinity, sarilumab blocks the binding of IL-6 and interrupts the cytokine-mediated signaling cascade. Interleukin-6 is a key element in the etiology of rheumatic conditions and inhibition of its signaling is a critical part of the mechanism of action of sarilumab.

For complete information on mechanism of action, summaries of animal and clinical studies, non-clinical and clinical pharmacokinetics, major route of elimination, safety profile, please see the Investigator's Brochure.

##### **5.1.1 Summary of nonclinical studies**

Sarilumab has been evaluated in a series of in vitro experiments to quantify the affinity of the antibody for IL-6R $\alpha$  and the ability to block the binding and signaling of IL-6. In addition, the role of the Fc effector function in the mechanism of action of the antibody was evaluated in vitro. The equilibrium binding affinity (KD) of sarilumab to human IL-6R $\alpha$  was determined by surface plasmon resonance (SPR) Biacore to be approximately 54 pM. Similar studies with cynomolgus monkey IL-6R $\alpha$  indicate a KD of 123 pM. The similar affinities of sarilumab for monkey and human IL-6R $\alpha$  indicate that monkeys are a relevant species for performing nonclinical studies. In contrast, no binding of sarilumab to murine IL-6R $\alpha$  was observed, suggesting that rodents are not a useful model system for pharmacology or toxicology studies. In vitro, sarilumab completely blocked the binding of a 200 nM concentration of human IL-6 to human IL-6R $\alpha$ , as demonstrated by SPR-Biacore; in a competition enzyme-linked immunosorbent assay, sarilumab blocked binding of a 100 pM constant concentration of dimeric human IL-6R $\alpha$  to human IL-6 with an IC50 of 108 pM. In vitro cell-based assays demonstrate that sarilumab blocks IL-6-dependent signal transducer and activator of transcription 3 (STAT3) activation in the HepG2 human hepatocarcinoma cell line, and blocks trans-signaling induced by a combination of IL-6 and soluble IL-6R $\alpha$  in an engineered human embryonic kidney 293 (HEK-293) cell line that overexpresses gp130 but does not express IL-6R $\alpha$ . No detectable Fc effector function activity was associated with sarilumab, as determined in vitro in cell-based assays for antibody-dependent cell-mediated cytotoxicity and complement-

dependent cytotoxicity. In total, these in vitro data are consistent with sarilumab exerting its actions through blockade of the IL-6/IL-6R $\alpha$  interaction.

Sarilumab does not bind to mouse IL-6R; therefore, the surrogate REGN844 antibody (an IL-6R antibody that cross reacts with mouse receptor) was used for the murine model experiments. In vitro, REGN844 binds specifically to mouse IL-6R $\alpha$  with high affinity and inhibits IL-6 stimulated mouse B-cell proliferation. A study with sarilumab was performed in double-humanized (IL-6hu/hu IL-6R $\alpha$ hu/hu) mice expressing human IL-6 and the human ectodomain of IL-6R $\alpha$  instead of the equivalent mouse gene products. In double-humanized IL-6/IL-6R $\alpha$  mice, sarilumab prevents turpentine-induced elevation of serum amyloid A (SAA), a key biomarker of the acute phase inflammatory response. For studies in wild type mice, REGN844 was tested. In concordance with the PD activity of sarilumab in double-humanized mice, REGN844 prevents turpentine-induced elevation of SAA and mitigated disease incidence, severity and bone erosion in a collagen induced arthritis model.

### **5.1.2 Summary of clinical studies**

As of 12 January 2018, the global sarilumab RA clinical development program consisted of 10 Phase 1 clinical pharmacology studies and 9 Phase 2/3 studies.

#### *Phase 1 studies:*

Of the 10 Phase 1 clinical pharmacology studies, 8 studies were conducted in patients with RA receiving methotrexate (MTX) and 1 study was conducted in healthy subjects. All but 2 of these studies (TDR10805/6R88-RA-0802 and INT12684) were single dose studies.

#### *Phase 2/3 studies in RA:*

Of the 9 Phase 2 and 3 studies of the global RA program, 5 studies have been completed (EFC11072/SARIL-RA-MOBILITY, EFC10832/SARIL-RA-TARGET, SFY13370/SARIL-RA-ASCERTAIN, EFC13752/SARIL-RA-ONE, MSC12665/SARIL-RA-EASY); 2 were prematurely terminated (ACT11575 and EFC11574/SARIL-RA-COMPARE) due to the operational feasibility and lack of ability to provide a timely result versus the plan but not due to any safety issue; and 2 studies are ongoing: the open-label extension part of EFC14092/SARIL-RA-MONARCH (double-blind part of this study has been completed) and the uncontrolled extension Phase 3 study LTS11210 (SARIL-RA-EXTEND) that enrolled patients from studies EFC11072, EFC10832, EFC13752, SFY13370, and ACT11575.

The global RA program has enrolled patients with RA from over 40 countries worldwide, who required alternatives to oral disease-modifying anti-rheumatic drugs (DMARDs) or tumor necrosis factor alpha (TNF- $\alpha$ ) antagonists because of inadequate control of disease activity or intolerance to these agents. This program entered Phase 2/3 with an operationally seamless study, EFC11072, consisting of a combined dose-ranging (Phase 2) part and a confirmatory (Phase 3) part, which was conducted in patients with active RA who were inadequate responders to MTX therapy.

In the dose-ranging part of the study (EFC11072/Part A), 5 dose regimens (100 mg q2w, 150 mg q2w, 200 mg q2w, 100 mg every week [qw], and 150 mg qw) and placebo were tested in 306 randomized patients. The demographic and disease characteristics at baseline were similar

across all treatment groups.

Based on an in-depth analysis of the Phase 2 study results, the 150 mg q2w and 200 mg q2w doses were selected for evaluation in 2 pivotal Phase 3 trials in RA (EFC11072 Part B and EFC10832) where sarilumab was tested as a combination therapy with a conventional DMARD.

In the Phase 3 confirmatory part of EFC11072 (Part B), both sarilumab dose groups showed clinically relevant and statistically significant ( $p<0.0001$ ) improvements compared with placebo in all 3 co-primary endpoints: improvement in signs and symptoms of RA at 24 weeks (as defined by 20% improvement on American College of Rheumatology [ACR] definition of improvement criteria [ACR20]), improvement in physical function (as assessed by Health Assessment Questionnaire Disability Index [HAQ-DI]) at Week 16 and inhibition of progression of structural damage at Week 52. Study EFC11072 Part B, Cohort 2 (where patients were randomized to either placebo or one of 2 selected doses: 150 mg q2w or 200 mg q2w) demonstrated that sarilumab 200 mg q2w and 150 mg q2w inhibited the 1-year rate of radiographic progression by 91% and 68% relative to placebo, respectively.

In addition to study EFC11072, efficacy of sarilumab was demonstrated in study EFC10832, conducted in patients who had an inadequate response or intolerance to one or more TNF- $\alpha$  antagonists. For the primary endpoints of ACR20 at Week 24 and HAQ-DI at Week 12, significant improvement was observed in patients treated with sarilumab 200 mg q2w and 150 mg q2w compared with placebo, showing that patients who previously had an inadequate response or intolerance to TNF- $\alpha$  antagonists responded to treatment with sarilumab.

Although demonstration of efficacy was not the primary objective for the other Phase 3 clinical trials in RA where sarilumab was administered either as monotherapy (EFC13752, EFC14092) or with concomitant DMARD therapy (SFY13370 and MSC12665), clinical efficacy profiles in these studies were consistent with results from the active-controlled Phase 3 studies in the global program (EFC11072 Part B, and EFC10832).

Patients who completed studies EFC11072, EFC10832, EFC13752, and SFY13370 had the option to enroll in the ongoing long-term extension study LTS11210 at the highest tested dose (200 mg q2w). In this study, the efficacy of sarilumab administered concomitantly with DMARDs was sustained for the duration of the available follow-up period: approximately 3.8 years and 2.1 years for patients initially randomized in EFC11072 Part B and EFC10832, respectively. The persistence of efficacy was consistent across all the domains of treatment of RA, namely signs and symptoms, structural damage, and physical function.

#### *Safety:*

For the patients treated with sarilumab and concomitant DMARD, a higher incidence of treatment-emergent adverse events (TEAEs), serious adverse events (SAEs), and TEAEs leading to discontinuation were observed in the sarilumab treatment groups compared to the placebo group. The incidence of TEAEs leading to death was similar in sarilumab and placebo groups.

In the placebo-controlled population, compared to the placebo group, higher incidences of

TEAEs, SAEs, and TEAEs leading to discontinuation were observed in sarilumab 200 mg q2w or 150 mg q2w + DMARD treatment groups relative to the placebo + DMARD group. These differences were generally attributable to higher rates of the AESIs associated with IL-6 blockade, specifically infections and laboratory abnormalities (including decrease in absolute neutrophil count (ANC) and platelet count, increase in transaminase and lipids) in the sarilumab + DMARD groups.

The observations with regards to adverse event (AE) and laboratory parameters with long-term administration were consistent with what was observed in the placebo-controlled population, and no safety findings were identified as attributable to long-term administration.

*Other diseases:*

Sarilumab was studied in ankylosing spondylitis (AS) patients in the DRI11073 study. Patients who completed the DRI11073 study had the possibility of enrolling in the LTS11298 long-term safety study if appropriate. The DRI11073 study failed to demonstrate clinical efficacy and the clinical development in this indication has been terminated. Consequently the LTS11298 study was prematurely discontinued. Overall, the safety observations from these studies conducted in patients with AS were consistent with what has been observed in patients with RA.

Sarilumab was also evaluated in a randomized double-blind Phase 2 study of patients with noninfectious uveitis (NIU) (ACT13480/SARIL-NIU-SATURN). Although the primary efficacy endpoint of a 2 step reduction in vitreous haze (VH) or reduction in steroid dose was not met, significant improvements were observed for key secondary endpoints such as change from baseline in adjudicated VH at Week 16, change from baseline in best-corrected visual acuity (BCVA) at Week 16, and change from baseline central retinal thickness (CRT) at Week 16. Furthermore, changes in adjudicated VH, BCVA, and CRT were maintained at Week 52. No new safety signals have been detected with sarilumab use in NIU compared with other indications. The AEs and laboratory changes were consistent with results observed in studies with sarilumab in RA patients and with IL-6 inhibition.

### **5.1.3 Intervention**

In Period 1, patients will all receive sarilumab in an open-label fashion. They will be provided with prefilled syringes containing 1.14 mL of sarilumab (equally 200mg), which they will administer subcutaneously every two weeks. This dose was chosen based on studies in rheumatoid arthritis that showed efficacy at this dose, and this is the FDA approved dose for the treatment of rheumatoid arthritis. In Period 2 of the study, patients will be randomized to withdraw from sarilumab and receive placebo or continue sarilumab. Sarilumab and placebo will be provided in identically matched glass prefilled syringes. Each prefilled syringe will contain 1.14 mL of sarilumab or matching placebo.

### **5.2 Availability**

Sarilumab and matching placebo will be provided by Regeneron.

### **5.3 Agent Ordering**

Study IP and matching placebo will be sent from Regeneron to the Stanford University Hospital investigational pharmacy where it will be appropriately stored in a locked facility. The drug shipment address is Stanford Health Care, Attention: Investigational Drug Service, [name]. [contact].

### **5.4 Agent Accountability**

All investigational drug supplies will be kept in appropriate, secure area (a locked refrigerator in the locked pharmacy room) under the responsibility of the Stanford Investigational Pharmacy and will be stored separately from other medication and in the original carton as per specification mentioned on the label.

## **6. DOSE MODIFICATIONS**

Sarilumab will be provided as a subcutaneous injection of 200 mg every two weeks. There will be no dosage modifications.

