- (17.) Patients with any of the following laboratory abnormalities at the screening visit: hemoglobin  $<$  8.5 g/dL, white blood cells  $<$  3000/mm^3, neutrophils  $<$  2000/mm^3, platelet count  $<$  150,000 cells/mm^3, aspartate aminotransferase (AST) or ALT  $>$  1.5 x ULN, and/or bilirubin (total) above the upper limit of normal (unless Gilbert's disease has been determined by genetic testing and documented).
- (18.) Presence of severe uncontrolled hypercholesterolemia ( $>$  350 mg/dL, 9.1 mmol/L) or hypertriglyceridemia ( $>$  500 mg/dL, 5.6 mmol/L) at screening or baseline.
- (19.) Patients with calculated creatinine clearance  $<$  30 mL/minute (using Cockcroft-Gault formula).
- (20.) History of alcohol or drug abuse within 5 years prior to the screening visit.
- (21.) Participation in any clinical research study evaluating another investigational drug or therapy

within 5 half-lives or 60 days of first investigational medicinal product (IMP) administration, whichever is longer.

(22.) Any patient who has had surgery within 4 weeks prior to the screening visit or with planned surgery during the course of the study.

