## **7. ADVERSE EVENTS AND REPORTING PROCEDURES**

### **7.1 Potential Adverse Events**

The adverse drug reactions in Phase 3 trials (i.e., events potentially associated with sarilumab administration) are upper respiratory tract infection, nasopharyngitis, oral herpes, urinary tract infection, neutropenia, leukopenia, thrombocytopenia, hypertriglyceridemia, injection site erythema, injection site rash, rash, urticaria, increased aspartate aminotransferase, and increased ALT.

Based on the preclinical and clinical studies of sarilumab as well as the safety profile of another IL-6 inhibitor (tocilizumab) and other biological DMARDs, hypersensitivity reactions, serious infections, and neutropenia, are an important identified risk with sarilumab administration. Important potential risks are thrombocytopenia and the potential risk of bleeding, clinically evident hepatic injury, an impact on CV outcome (MACE) secondary to LDL elevation, GI perforations, and malignancy.

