### **7.2 Adverse Event Reporting**

All AEs regardless of seriousness or relationship to IMP/NIP, spanning from the signature of the informed consent form, until the end of the study as defined by the protocol for that patient, are to be recorded on the corresponding page(s) or screen(s) included in the CRF. Whenever possible, diagnosis or single syndrome should be reported instead of symptoms. The Investigator should specify the date of onset, intensity, action taken with respect to IMP, corrective treatment/therapy given, additional investigations performed, outcome and his/her opinion as to whether there is a reasonable possibility that the AE was caused by the IMP. Laboratory, vital signs or ECG abnormalities are to be recorded as AEs only if they are medically relevant: symptomatic or requiring either corrective treatment or consultation or leading to discontinuation or modification of

dosing and/or fulfilling a seriousness criterion and/or is defined as an AE with pre-specified monitoring.

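### After the first dose, no neutrophil, platelet or AST/ALT result is tied to holding or stopping study drug in an individual patient

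*Combined protocol and SAP*

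**What the plan says.** Before treatment, exclusion criterion 17 in Section 3.2 lists "laboratory abnormalities at the screening visit" that bar entry: neutrophils below 2000/mm3, platelets below 150,000/mm3, and AST or ALT above 1.5 x ULN.

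After the first dose, Section 6 gives a fixed 200 mg every two weeks and states: "There will be no dosage modifications". Section 4.2, which is headed as the criteria for removal, places the study on hold for a death, a drug-related serious adverse event, "or a Grade 4 treatment emergent adverse event or laboratory" abnormality. It continues: "The safety monitoring committee will determine if the study can resume and if the patient should remain in the study or be removed". The only other route off study in that section is the patient's own: "A patient may withdraw from the study at any time if they choose to withdraw their consent".

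Section 7.2 tells the investigator to record the action taken with study drug. It counts as an adverse event a laboratory abnormality "leading to discontinuation or modification of" dosing, or one that "is defined as an AE with pre-specified monitoring". No such pre-specified events are listed. The study calendar has early-termination and unscheduled-visit columns.

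On risk, Section 7.1 says that hypersensitivity reactions, "serious infections, and neutropenia, are an important identified risk with sarilumab administration". It lists thrombocytopenia and hepatic injury as important potential risks.

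**The concern.** These are the drug's own known laboratory effects. The safety summary in Section 2.2 reports more neutrophil, platelet and transaminase abnormalities on sarilumab plus DMARD than on placebo plus DMARD, and Section 4.1 lets patients here stay on DMARDs. For a clear but non-serious fall in counts or rise in transaminases below Grade 4, the protocol does not say when to retest, hold, resume or stop. Two investigators could treat the same value differently, in a trial that calls safety an important secondary objective (Section 1.2).

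The gap also reaches the analysis. The protocol does not say whether a patient taken off drug for safety in Period 1 is a responder, or what follow-up applies to one taken off in Period 2.

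**Working it through.** The plan gives no figure to reproduce. The check sets the relevant sections side by side.

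**1. Limits before and after the first dose**

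| Test | Screening limit (3.2) | Level after first dose | Status in 7.1 |
|---|---|---|---|
| Neutrophils | 2000/mm3 | none | identified risk |
| Platelets | 150,000/mm3 | none | potential risk |
| AST/ALT | 1.5 x ULN | none | potential risk (hepatic injury) |

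Count: 3 limits at screening, 0 afterwards.

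**2. Triggers in Section 4.2.** There are three: death, drug-related serious event, and Grade 4 event or laboratory abnormality. All three act on the whole study. A patient-level decision follows a hold, made by the committee without a stated criterion. No grading scale is named anywhere in the document.

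**3. Timing of checks against doses.** The calendar schedules blood count and chemistry at Weeks 2, 4, 8, 12, 16, 18, 20, 24, 28 and 34, which is ten post-baseline checks. From baseline to Week 28 the gaps are 2, 2, 4, 4, 4, 2, 2, 4 and 4 weeks, so the longest is 4 weeks. Patients inject themselves every 2 weeks (5.1.3), so a four-week gap holds 4 / 2 = 2 injections. If dosing starts at baseline and stays on even weeks, one is on the visit day and one is midway. After an abnormal Week 8 value, for example, the Week 10 injection comes before the Week 12 check unless someone intervenes. An unscheduled visit is available, but no result calls for one.

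**4. Board meetings.** Treatment to Week 28 is 28 x 7 = 196 days, and 196 / 30.44 = 6.4 months. The board meets every 6 months (4.3), so usually one scheduled meeting falls within a patient's treatment. Event-driven review exists for the 4.2 triggers, and serious events go to the committee within 24 hours (7.2.1). A non-serious value below Grade 4 activates neither.

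**5. Safety stops in the analysis.** Section 12.1 makes a Period 1 patient a non-responder for failing the taper, receiving rescue, or stopping drug in order to start another therapy. The synopsis adds a violation of the taper. A patient stopped for safety who completes the taper without rescue meets none of these. Section 5.1.3 speaks of continuing sarilumab in Period 2, which implies that randomized patients are still on it, but no sentence excludes this patient. In Period 2, a flare is rescue or a switch of therapy. A safety stop alone is neither, and follow-up after it is not stated. With 12 randomized (12.3), an arm is about 12 / 2 = 6, so one such patient is 1 / 6 = 16.7% of it.

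**The case against.** The strongest reply is that the protocol is less bare than Section 6 looks when read alone. The no-modification sentence follows a fixed dose and reads naturally as ruling out other dose levels. Section 7.2 and the early-termination column show that stopping one patient is foreseen. Blood is checked ten times after baseline. Section 4.3 gives the board all data, and Section 4.2 gives the committee an explicit decision on the individual patient. Section 5.1 points to the Investigator's Brochure for the safety profile, and the Brochure may contain action limits. On the analysis side, only Period 1 responders are randomized, and the primary analysis is already by intention to treat.

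Most of this stands. A reader might infer from Sections 4.2 and 6 together that the investigator must go on giving full dose through a marked abnormality. The documents do not support that: nothing forbids an investigator from stopping, and the recording rules assume that it can happen. Nor is the board shut out.

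What the reply does not supply is a level. The wording in 7.2 governs what is recorded, not when to act. Section 5.1 refers to the Brochure for information and does not adopt dosing or stopping rules from it. The committee's patient-level decision is described only after a study hold. Intention to treat keeps a randomized patient in the analysis, but does not say whether a patient already stopped for safety should be randomized.

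**Conclusion.** The point holds as a gap in patient-level safety guidance that should be closed. Three laboratory tests tied to risks named in 7.1 have entry limits and no on-treatment limits. Below Grade 4, on an unstated scale, action is left entirely to judgement. One injection can fall between scheduled checks. The analysis consequence is limited to patients stopped for safety, each worth about 17% of a Period 2 arm if six are randomized per arm.

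The absence of limits and of a scale rests on the text alone. Whether investigators have limits from the Brochure cannot be seen here. No event rate is assumed and no estimate of harm is made. A reader might also be tempted to size the gap as the distance from the screening limit to Grade 4. The documents do not support such a figure, because no scale is named and an entry limit is not a level at which one would hold drug. The gap does not invalidate the primary comparison.

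**What to change.** 1. **Section 6.** State that the 200 mg dose will not be reduced, but that the investigator may interrupt or permanently stop study drug in any patient for safety.

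2. **Section 4.2.** Name the grading scale. Add patient-level hold and stop limits with a retest within 1 week, taken from the Investigator's Brochure if it gives them. Otherwise the values below are a reviewer's assumption, with a plausible range in brackets:

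| Test | Hold and retest | Stop if confirmed |
|---|---|---|
| Neutrophils (/mm3) | <1000 (1000 to 1500) | <500 (500 to 750) |
| Platelets (/mm3) | <100,000 (75,000 to 100,000) | <50,000 (40,000 to 60,000) |
| AST/ALT (x ULN) | >3 (2.5 to 4) | >5 (5 to 8) |

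   Resume 200 mg when the retest is back within the hold limit. State a maximum hold duration, to be set by the sponsor. State also that the patient-level stop applies even where the same value triggers the Grade 4 study hold, so that the two rules do not conflict. List these events in 7.2 as those with pre-specified monitoring. Apply the rules to study drug in both Period 2 arms alike.

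3. **Section 12.1.** State that a patient permanently stopped for safety in Period 1 is a non-responder and is not randomized, and that one stopped in Period 2 stays in the intention-to-treat analysis and is followed to Week 28 for flare.

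The change is wording only, and uses bloods already drawn and the existing unscheduled visit. The cost is some retest visits and missed doses. In Period 2, 12 weeks at one injection every two weeks is 12 / 2 = 6 injections, so each missed dose in the sarilumab arm is a partial withdrawal of about one sixth. This is a reason to keep the maximum hold short.
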